4.5.5 C-SSRS Data

The Columbia Suicide Severity Rating Scale (C-SSRS) is an assessment that evaluates suicidal ideation and behavior. There are 5 “Yes/No” questions on suicidal ideation following the increasing severity order: (1) Wish to be dead, (2) Non-specific active suicidal thoughts, (3) Active suicidal ideation with any methods (not plan) without intent to act, (4) Active suicidal ideation with some intent to act, without specific plan, (5) Active suicidal ideation with specific plan and intent, and 6 “Yes/No” questions on suicidal behavior following the increasing severity order: (6) Preparatory acts or behavior, (7) Aborted attempt, (8) Interrupted attempt, (9) Actual attempt, (10) Suicidal behavior, (11) Suicide (only at post-baseline visits). Another “Yes/No” question of whether the subject has engaged in non-suicidal self-injurious behavior is also collected.

In the summary table for C-SSRS, number of subjects who answered “Yes” to each of the 11 questions post-baseline, subjects who answered “Yes” to at least one question for suicidal ideation, subjects who answered “Yes” to at least one question for suicidal behavior, and subjects who have engaged in non-suicidal self-injurious behavior will be presented. A listing of subjects with any suicidal ideation or behavior at baseline or post-baseline will be provided.

4.5.6 ECG Data

Shift from normal or unknown ECG at baseline to abnormal, not adverse event or abnormal, adverse event post-baseline ECG will be summarized for the placebo-controlled period. Subjects with abnormal post-baseline ECG status will be listed.

4.5.7 Vital Sign Data

Vital sign parameters include body temperature, systolic blood pressure, diastolic blood pressure, heart rate, respiration rate and weight. Vital signs will be measured with the subject supine and after the subject has been resting for at least 10 minutes. The descriptive statistics for actual values and change from baseline will be summarized at each visit. Plot of mean vital sign values at each visit will be provided.

The analysis of vital signs will also focus on the incidence of clinically relevant outliers based on the following criteria. The incidence and percentage of clinically relevant outliers determined by each criterion will be summarized. A listing of subjects with clinically relevant vital signs will be provided.

Table 9: Criteria Used to Assess Potential Clinically Relevant Outliers in Vital Signs

Variable	Low	High
Systolic Blood Pressure	<90 mm Hg or ≥ 20 mm Hg decrease from Baseline (BL)	>180 mm Hg or ≥ 20 mm Hg increase from BL

CONFIDENTIAL

The information contained herein may not be used, disclosed, or published without the written consent of Biogen MA Inc.

Diastolic Blood Pressure	< 50 mm Hg or ≥ 15 mm Hg decrease from BL	>105 mg Hg or ≥ 15 mm Hg increase from BL
Heart Rate	<50 bpm or ≥ 15 bpm decrease from BL	>120 bpm or ≥ 15 bpm increase from BL
Temperature	>2 degree C decrease from BL	>38.5 C or >2 degrees C increase from BL
Respiration Rate	< 10 breaths per minute or $\geq 50\%$ decrease from BL	>25 breaths per minute or $\geq 50\%$ increase from BL
Weight	$\geq 7\%$ decrease from BL	$\geq 7\%$ increase from BL

BL= baseline; bpm = beats per minute

Visit windows for by visit summaries

For vital sign by visit summaries, the analysis visit should be defined using windows (see Table 10 below). If there is more than 1 value in the same analysis visit window for a certain parameter for a subject, then the closest record to the target visit day will be used for the by visit analysis. If there are 2 values in the same analysis visit window with the same distance from the target visit day for a certain parameter for a subject, then the record with the later date will be used for the by visit analysis.

Table 10: Visit Windows for Vital Sign by Visit Summaries

Analysis visit	Target visit day	Analysis visit window
Baseline	1	Most recent non-missing pre-dose value
Week 4	29	[2, 42]
Week 8	57	[43, 70]
Week 12	85	[71, 98]
Week 16	113	[99, 126]
Week 20	141	[127, 154]
Week 24	169	[155, 182]
Week 28	197	[183, 210]
Week 32	225	[211, 238]
Week 36	253	[239, 266]
Week 40	281	[267, 294]
Week 44	309	[295, 322]
Week 48	337	[323, 350]
Week 52	365	[351, 378]
Week 56	393	[379, 406]
Week 60	421	[407, 434]
Week 64	449	[435, 462]
Week 68	477	[463, 490]
Week 72	505	[491, 518]
Week 76	533	[519, the end day of the placebo-controlled period*]

* The end day of the placebo-controlled period is the last day before the first infusion in LTE for subjects who enter LTE, and is the last day in study for subjects who do not enter LTE.

4.6 Pharmacokinetics Analysis

The PK analysis population will be used for the description of the concentration-time profiles and for the estimation of PK parameters. Randomization treatment groups will be used for

CONFIDENTIAL

The information contained herein may not be used, disclosed, or published without the written consent of Biogen MA Inc.

PK analysis. Tables and figures, if not otherwise specified, will be presented by treatment group stratified by ApoE status (3 columns under each treatment group: ApoE ϵ 4+, ApoE ϵ 4- and total; analysis display B in Appendix 6.1). Listings will be presented by treatment group stratified by ApoE status.

PK evaluation will be based on the concentration of aducanumab in serum samples collected prior to infusion and between 10 and 60 minutes after completion of the infusion and line flush for the visits specified per protocol.

Concentrations of aducanumab that are below the limit of quantification (BLQ) will be imputed as 0. When summarizing concentrations or PK parameters in serum, a minimum of 2 values are required to show the arithmetic mean and geometric mean, and at least 3 values are required to show the standard deviation and coefficient of variation.

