4.6.1 Serum Concentration Profile

Serum concentration data will be summarized by nominal visit. Number of evaluable subjects, arithmetic mean, standard deviation, median, 25% and 75% quartiles, minimum, maximum, geometric mean, and coefficient of variation will be presented at each visit. A listing of individual concentration data will be provided.

A semi-logarithmic plot of the mean serum concentration-time curves of aducanumab from first visit to last visit through nominal times will be provided.

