4.6.2 Serum PK Parameters

Two PK parameters C_{max} and C_{min} will be computed by noncompartmental methods, as data permit, from serum concentration-time data:

Parameter	Definition	Units
C_{max}	Observed maximum serum aducanumab concentration	ug/mL
C_{min}	Observed minimum serum aducanumab concentration	ug/mL

Number of evaluable subjects, arithmetic mean, standard deviation, median, 25% and 75% quartiles, minimum, maximum, geometric mean, and coefficient of variation will be presented for the PK parameters.

4.6.3 Subgroup analysis for protocol version 4

Due to the change in maximal dose from 6 mg/kg to 10 mg/kg for ApoE ϵ 4 carrier high dose group in protocol version 4, not all subjects have had opportunity to receive the protocol specified high dose (6 doses in titration before receive 10mg/kg) in the placebo-controlled period. Summary tables for serum concentration and PK parameters will be provided for ApoE ϵ 4 carriers who were randomized to the high dose group, stratified by the expected number of doses at 10 mg/kg (categories of 0, 1-6, 7-13, 14, and a total column of having at least one dose) a subject would have received based on the first infusion date and the date consenting to protocol version 4.

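### Setting every BLQ concentration to 0 conflicts with the planned geometric means, and the unrestricted Cmin becomes 0 for any subject with a drug-free sample

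*SAP*

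**What the plan says.** Placebo-controlled SAP, Section 4.6: "Concentrations of aducanumab that are below the limit of quantification (BLQ) will be imputed as 0". No exception is made for any statistic. The same section sets a display condition, "a minimum of 2 values are required to show the arithmetic mean and geometric mean", which says nothing about zeros. PK evaluation uses "serum samples collected prior to infusion and between 10 and 60 minutes after completion of the infusion", at visits left to the protocol.

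Section 4.6.1 lists statistics by nominal visit, ending with "geometric mean, and coefficient of variation will be presented at each visit". It adds: "A semi-logarithmic plot of the mean serum concentration-time curves of aducanumab from first visit to last visit through nominal times will be provided". It does not say whether the plotted mean is arithmetic or geometric.

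Section 4.6.2 names two parameters, Cmax and Cmin. Cmin is defined as "Observed minimum serum aducanumab concentration", with no visit, dosing interval or post-dose restriction. The same statistics follow: "geometric mean, and coefficient of variation will be presented for the PK parameters".

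The LTE SAP repeats the BLQ rule in Section 3.6. Section 3.6.1 plans geometric means by visit over both the placebo-controlled and LTE periods, and Section 3.6.2 repeats the Cmin definition. It plans no semi-logarithmic plot.

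In both SAPs (Sections 4.1.1 and 3.1.1) the PK population requires at least one measurable concentration per subject.

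**The concern.** A geometric mean cannot absorb a zero, yet the plan creates zeros by rule and then asks for geometric means. This goes beyond missing detail, because a programmer who follows the text obtains an unusable number. The alternative is to improvise, most likely by letting log(0) become missing, which drops the lowest values without trace.

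Cmin has a related defect. A minimum over all serum samples includes any sample taken before the subject had received drug. Such a sample is expected to be BLQ, is set to 0, and becomes the minimum whatever the later troughs were.

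Serum concentrations and PK parameters are a named tertiary endpoint (Section 1.3.2), and Cmax and Cmin are the only two parameters. Section 4.6.3 uses them to describe high-dose ApoE ε4 carriers by expected number of 10 mg/kg doses. A Cmin fixed at 0 cannot distinguish those strata.

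**Working it through.** The plan gives no figure to reproduce, no LLOQ and no expected BLQ rate. The concentrations, LLOQ values and BLQ rates below are therefore assumptions for illustration.

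**1. Geometric mean.** GM = (∏xᵢ)^(1/n) = exp(mean of ln xᵢ). One xᵢ = 0 gives 0 in the product form and an undefined result in the log form. The illustration uses 500 simulated lognormal values (centre 20 µg/mL, log-SD 0.5). With no BLQ value, GM = 19.6. With 1 of 500 set to 0, GM = 0 or undefined.

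**2. Dropping zeros instead.** With k of n values BLQ and the measurable values having geometric mean G, substituting LLOQ/2 gives exp{[(n−k)·ln G + k·ln(LLOQ/2)]/n}.

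- k = 25, G = 19.63, LLOQ 0.1: exp(0.95 × 2.977 + 0.05 × ln 0.05) = exp(2.828 − 0.150) = 14.6. With LLOQ 1: exp(2.828 − 0.035) = 16.3. Dropping the zeros reports 19.6.
- k = 100, G = 19.74: 6.0 (LLOQ 0.1) or 9.5 (LLOQ 1). Dropping the zeros reports 19.7.

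Dropping zeros therefore hides the BLQ values and overstates the geometric mean.

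**3. How often a cell is hit.** P(at least one BLQ value) = 1 − (1 − p)ⁿ. Here n = 535 is the planned group size (Section 3) and n = 150 is an assumed smaller cell.

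| Assumed BLQ rate p | n = 535 | n = 150 |
|---|---|---|
| 0.1% | 41% | 14% |
| 0.5% | 93% | 53% |
| 1% | 99.5% | 78% |
| 5% | about 100% | 99.95% |

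A cell with no BLQ value is unaffected.

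**4. Semi-logarithmic plot.** The arithmetic mean is positive unless every value is BLQ. With 100 of 500 at 0 it is 17.6 (log₁₀ = 1.25) and can be plotted. With 500 of 500 at 0 it is 0 and cannot. A geometric-mean curve would fail at every visit with any BLQ value.

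**5. Cmin and Cmax.** min(0, later values) = 0. In a simulation with six troughs per subject (same assumed distribution, peaks at eight times trough), adding one drug-naive zero gives Cmin = 0 for every subject. The geometric mean is then 0 or undefined, and the CV is 0/0. Without that sample the median Cmin is 10.9. The geometric mean of Cmax is 307.1 either way, because every PK-population subject has a measurable value.

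**6. Where drug-free samples can arise.**

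- *LTE SAP.* Late-start subjects received saline in the placebo-controlled period (Table 1) and join the PK population through later measurable values. Section 3.6.1 tabulates placebo-period concentrations by LTE group. If these subjects were sampled then, those columns are expected to be BLQ and so set to 0, and Section 3.6.2 gives these subjects Cmin = 0.
- *Placebo-controlled SAP, active arms.* The effect requires a PK sample before the first dose. Collection before infusion is compatible with one, but it also fits later visits only.
- *Placebo-controlled SAP, placebo column.* Section 4.5.1 foresees accidental active doses in placebo subjects, and PK uses randomized groups. If such a subject was sampled before that dose, the same result follows.

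**The case against.** The strongest reply is that the PK visits sit in the protocol, which is not shown, so the SAP does not establish that any sample precedes the first dose. For the active arms in the placebo-controlled SAP this stands. A reader might infer that Cmin is 0 for nearly every subject in every arm and carries no information on troughs. The document does not support that: the pre-first-dose sample is unconfirmed, and placebo subjects without a measurable concentration are not in the PK population.

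A reader might also infer that the semi-logarithmic plot fails in general. It does not. If the arithmetic mean is plotted, only an all-BLQ time point cannot be drawn.

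The consequences are also limited. Cmax is unaffected. By-visit arithmetic means, medians, quartiles and extremes remain computable and individual concentrations are listed, so trough exposure can be read without Cmin. No PK hypothesis test is planned, and no efficacy or safety conclusion depends on these tables. The BLQ frequency is unknown, and LLOQ/2 is only a convention.

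The central point remains. The zero rule has no exception, the geometric means are required, and Cmin has no sampling restriction. The LTE case does not depend on a Day 1 sample, only on former placebo subjects having been sampled during the placebo-controlled period.

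**Conclusion.** The point holds in limited form. In both SAPs the BLQ rule is incompatible with the planned geometric means wherever a cell contains at least one BLQ value: the result is 0 or undefined, or biased upward if zeros are dropped. The open Cmin definition returns 0 for any subject with a drug-free BLQ sample.

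The number of affected cells cannot be stated from the documents; under the assumed rates the chance per cell runs from 14% to about 100%. The Cmin effect rests on placebo-period sampling of late-start subjects in the LTE SAP, and on an unconfirmed pre-first-dose sample for the active arms in the placebo-controlled SAP. The damage is confined to descriptive tertiary output. It is worth correcting because the stated rule gives a wrong number when followed and the correction is cheap.

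**What to change.** In both SAPs:

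- Keep BLQ = 0 for arithmetic summaries only.
- For geometric means, state a non-zero substitution for BLQ values after the first active dose, for example LLOQ/2. Report the BLQ count in each cell, and show no geometric mean where most values are BLQ.
- Define Cmin from pre-infusion samples after the first active dose, tied to a stated visit or dosing interval, and exclude drug-naive and placebo-period samples. Restricting Cmin to post-first-dose samples alone is not enough: Table 1 starts all active groups on the same titration doses, so an early trough could still determine the minimum.

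In the placebo-controlled SAP only, state which mean is drawn on the semi-logarithmic plot.

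The cost is a few sentences in Sections 4.6 to 4.6.2 and in LTE Sections 3.6 to 3.6.2. The one drawback is that the substitution value is a convention. It should be named in the table footnote, and the BLQ counts let a reader judge its influence.

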4.6.1 Serum Concentration Profile

Serum concentration data will be summarized by nominal visit. Number of evaluable subjects, arithmetic mean, standard deviation, median, 25% and 75% quartiles, minimum, maximum, geometric mean, and coefficient of variation will be presented at each visit. A listing of individual concentration data will be provided.

A semi-logarithmic plot of the mean serum concentration-time curves of aducanumab from first visit to last visit through nominal times will be provided.

4.6.2 Serum PK Parameters

Two PK parameters C_{max} and C_{min} will be computed by noncompartmental methods, as data permit, from serum concentration-time data:

Parameter	Definition	Units
C_{max}	Observed maximum serum aducanumab concentration	ug/mL
C_{min}	Observed minimum serum aducanumab concentration	ug/mL

Number of evaluable subjects, arithmetic mean, standard deviation, median, 25% and 75% quartiles, minimum, maximum, geometric mean, and coefficient of variation will be presented for the PK parameters.

4.6.3 Subgroup analysis for protocol version 4

Due to the change in maximal dose from 6 mg/kg to 10 mg/kg for ApoE ϵ 4 carrier high dose group in protocol version 4, not all subjects have had opportunity to receive the protocol specified high dose (6 doses in titration before receive 10mg/kg) in the placebo-controlled period. Summary tables for serum concentration and PK parameters will be provided for ApoE ϵ 4 carriers who were randomized to the high dose group, stratified by the expected number of doses at 10 mg/kg (categories of 0, 1-6, 7-13, 14, and a total column of having at least one dose) a subject would have received based on the first infusion date and the date consenting to protocol version 4.

4.7 Immunogenicity Analysis

4.7.1 Background

Definition of baseline value

Baseline value is defined as the latest immunogenicity data collected prior to the first dose. If no immunogenicity data are collected prior to the first dose, baseline value is missing and will be imputed as anti-drug antibody negative for immunogenicity analyses.

Treatment-emergent anti-aducanumab antibody positive responses

Post-baseline positive anti-aducanumab antibody responses are defined as treatment-emergent if a subject is either (1) antibody negative at baseline; or (2) antibody positive at baseline but the post-baseline antibody response is more than 2-fold increase in titer compared to the baseline response.

Persistent and transient positive responses for the placebo-controlled period

Subjects with treatment-emergent positive anti-aducanumab antibody responses in the placebo-controlled period will be further classified as transient positive, if only a single positive evaluation occurs or more than 1 positive evaluation but occur with < 112 days (16 weeks) apart, or as persistent positive, if more than one consecutive positive evaluation occurs \geq 112 days (16 weeks) apart or a positive evaluation occurs at the last available time point with no further negative results available (including long-term extension).

4.7.2 Immunogenicity analysis

Immunogenicity population will be used to analyze immunogenicity data. Safety treatment groups will be used for immunogenicity analysis. Tables will be presented by treatment group (placebo, low dose, high dose and BIIB037 total; analysis display A in Appendix 6.1). Listings will be presented by treatment group stratified by ApoE status.

A summary table of subjects with treatment-emergent positive anti-aducanumab antibody responses results will be provided. The number and percentage of anti-aducanumab positive responses will be summarized at each visit and at any time post-baseline. Subjects with persistent response and subjects with transient response will be presented. A listing of subjects with anti-aducanumab antibody positive results will also be provided.

Visit windows for by visit summaries

For immunogenicity by visit summaries, the analysis visit should be defined using visit windows (see Table 11Table 7 below). If there is more than 1 value in the same analysis visit window for a subject, then the closest record to the target visit day will be used for the by visit analysis. If there are 2 values in the same analysis visit window with the same distance

from the target visit day for a certain parameter for a subject, then the record with the later date will be used for the by visit analysis. If there are 2 values on the same day for a certain parameter for a subject, then the record with the later time will be used for the by visit analysis.

Table 11: Visit Windows for Immunogenicity by Visit Summaries

Analysis visit	Target visit day	Analysis visit window
Baseline	1	Most recent non-missing pre-dose value
Week 24	169	[2, 196]
Week 32	225	[197, 308]
Week 56	393	[393, 470]
Week 78	547	[470, the end day of the placebo-controlled period*]
* The end day of the placebo-controlled period is the last day before the first infusion in LTE for subjects who enter LTE, and is the last day in study for subjects who do not enter LTE.		

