4.5.4.1 Quantitative analyses

For numeric laboratory parameters, actual values, change from baseline and percent change from baseline will be summarized by visit. Number of evaluable subjects, mean, standard deviation, median, 25% and 75% quartiles, minimum and maximum values will be presented at each visit.

Plots of mean values (with standard error) for numeric laboratory parameters at each visit will be provided.

Listings of individual laboratory measurements by patients for all the parameters will be provided.

Visit windows for by visit summaries

For laboratory by visit summaries, the analysis visit should be defined using visit windows (see Table 7 below). If there is more than 1 value in the same analysis visit window for a certain parameter for a subject, then the closest record to the target visit day will be used for the by visit analysis. If there are 2 values in the same analysis visit window with the same distance from the target visit day for a certain parameter for a subject, then the record with the later date will be used for the by visit analysis. If there are 2 values on the same day for a certain parameter for a subject, then the record with the later time will be used for the by visit analysis.

Table 7: Visit Windows for Laboratory by Visit Summaries

Analysis visit	Target visit day	Analysis visit window
Baseline	1	Most recent non-missing pre-dose value
Week 24	169	[2, 252]
Week 48	337	[253, 420]
Week 72	505	[421, 525]

CONFIDENTIAL

The information contained herein may not be used, disclosed, or published without the written consent of Biogen MA Inc.

Analysis visit	Target visit day	Analysis visit window
Week 78	547	[526, the end day of the placebo-controlled period*]
* The end day of the placebo-controlled period is the last day before the first infusion in LTE for subjects who enter LTE, and is the last day in study for subjects who do not enter LTE.		

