3.7.2 Immunogenicity analysis

Immunogenicity population will be used to analyze immunogenicity data. LTE safety treatment groups will be used for immunogenicity analysis. Tables will be presented by LTE treatment group (late start low dose, late start high dose, early start low dose, early start high dose, and in addition late start total, early start total and BIIB037 total; analysis display A in Appendix 4.1). Listings will be presented by treatment group stratified by ApoE status.

A summary table of subjects with treatment-emergent positive anti-aducanumab antibody responses in the placebo-controlled and LTE active treatment period will be provided. The number and percentage of anti-aducanumab positive results will be summarized at each visit as well as at any time post-baseline in this period. Subjects with persistent response and

subjects with transient response in this period will be presented. A listing of immunogenicity data in placebo-controlled and LTE period for subjects with anti-aducanumab antibody positive results will also be provided.

Visit windows for by visit summaries

For immunogenicity by visit summaries, the analysis visit should be defined using visit windows (see Table 7 below). If there is more than 1 value in the same analysis visit window for a subject, then the closest record to the target visit day will be used for the by visit analysis. If there are 2 values in the same analysis visit window with the same distance from the target visit day for a certain parameter for a subject, then the record with the later date will be used for the by visit analysis. If there are 2 values on the same day for a certain parameter for a subject, then the record with the later time will be used for the by visit analysis.

Table 7: Visit Windows for Immunogenicity by Visit Summaries

Analysis visit	Analysis visit window ¹	
	For subjects who received the first dose of aducanumab in the placebo-controlled period	For subjects who received the first dose of aducanumab in the LTE period
Baseline	Last value prior to the first dose of aducanumab	Last value prior to the first dose of aducanumab
Week 24	[2, 196]	[2, 252]
Week 32	[197, 308]	NA
Week 56	[309, 470]	[253, 420]
Week 78	[471, end day of the placebo-controlled period ²]	[421, 609]
Week 80	[start day of the LTE period ³ , 644]	NA
Week 104	[645, 812]	[610, 1260]
Week 128	[813, 980]	NA
Week 152	[981, 1169]	NA
Week 182	[1170, 1820]	≥ 1261
Week 338	≥ 1821	NA

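### SAP Table 11 puts days 309–392 in no immunogenicity window and day 470 in two, so early Week 56 antibody samples drop from the by-visit row

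*SAP*

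**What the plan says.** Section 4.7.2 of the placebo-controlled SAP promises a by-visit antibody summary: "The number and percentage of anti-aducanumab positive responses will be summarized at each visit and at any time post-baseline". It assigns each sample to an analysis visit through the windows in Table 11. Three consecutive rows (visit, target day, window) matter here:

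- "Week 32 225 [197, 308"
- "Week 56 393 [393, 470"
- "Week 78 547 [470, the end day of the placebo-controlled period"

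The accompanying tie rules choose among several values that lie inside one window: nearest to target, then later date, then later time.

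The LTE SAP covers the same visits in its own Table 7 (Section 3.7.2). The column headed "For subjects who received the first dose of aducanumab in the placebo-controlled period" gives Week 56 as the first interval in "Week 56 [309, 470] [253, 420" and opens Week 78 at "471, end day of the placebo-controlled period".

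**The concern.** The Week 56 window has no room before its target day. A sample one day early has no visit, while one 77 days late does. Separately, day 470 is claimed by both Week 56 and Week 78. The tie rules help with neither fault, because they operate only within a single window.

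If the table is programmed literally, Week 56 samples drawn before day 393 disappear from the Week 56 count and percentage in all three arms. The main cost is precision; there is no claim of bias. A second cost is inconsistency: for early-start subjects the LTE report would count the same samples at Week 56, so two reports from one trial could show different Week 56 rows.

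**Working it through.** **Inputs.** Table 11 target days are 169, 225, 393 and 547. Its windows are [2, 196], [197, 308], [393, 470] and [470, end of the placebo-controlled period].

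**Coverage.** The number of windows containing each day was counted from day 2 to day 600.

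| Table | Days in no window | Days in two windows |
|---|---|---|
| Placebo-controlled SAP, Table 11 | 309–392: 392 − 309 + 1 = 84 days | 470 |
| LTE SAP, Table 7, early-start column | none | none |
| Placebo-controlled SAP, Table 7 (laboratory) | none | none |

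Day 470 is 470 − 393 = 77 days from the Week 56 target and 547 − 470 = 77 days from the Week 78 target. Extending the nearest-to-target rule across windows would therefore not settle it either.

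**What the lower bound should be.** Windows in this SAP open at the midpoint between adjacent target days:

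- Table 11, Week 32: (169 + 225)/2 = 197, as printed.
- Table 11, Week 78: (393 + 547)/2 = 470, as printed.
- Laboratory Table 7: (169 + 337)/2 = 253, the bound printed in "Week 48 337 [253, 420"; (337 + 505)/2 = 421; (505 + 547)/2 = 526.
- Efficacy Table 3: (183 + 351)/2 = 267; (351 + 547)/2 = 449.

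For Week 56 the rule gives (225 + 393)/2 = 309, the day after Week 32 closes and the value in the LTE SAP. The printed 393 repeats the target day from the adjacent cell.

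**Share of Week 56 samples lost.** This depends on when visits took place, which the SAP does not state. The figures below are assumptions, shown as a range.

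Even, symmetric spread of ±k days about day 393, share before target = k/(2k + 1):

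- ±3 days: 3/7 = 43%
- ±5 days: 5/11 = 45%
- ±7 days: 7/15 = 47%

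Normal timing, share before day 393 = Φ((−0.5 − shift)/SD), where shift is the mean number of days late:

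| Mean timing | SD 3 | SD 5 | SD 7 | SD 10 | SD 14 |
|---|---|---|---|---|---|
| 3 days early | 0.80 | 0.69 | 0.64 | 0.60 | 0.57 |
| On target | 0.43 | 0.46 | 0.47 | 0.48 | 0.49 |
| 3 days late | 0.12 | 0.24 | 0.31 | 0.36 | 0.40 |
| 7 days late | 0.01 | 0.07 | 0.14 | 0.23 | 0.30 |
| 14 days late | 0.00 | 0.00 | 0.02 | 0.07 | 0.15 |

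**What is untouched.** The any-time summary and the listing do not refer to windows. The persistent/transient classification in Section 4.7.1 uses the interval between positive samples (112 days), not analysis visits.

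**The case against.** The strongest reply is that this is an obvious slip. The bound duplicates its neighbour, the companion LTE plan prints the intended value, and a programmer would probably query it. That is fair as to likelihood. But Table 11 is the operative rule, the LTE SAP does not amend it, and a programmer who corrects it unprompted departs from a final SAP.

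A second point is that the midpoint convention does not lead to the LTE boundary at day 470. Strictly applied, it gives Week 56 as [309, 469] and leaves Week 78 opening at 470. This is correct: either version removes both faults, and they differ by one day. The LTE version has the advantage of making the two plans agree.

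Third, a range of about 0–80% says little. That also stands: only the day counts are documented, and the percentages should not carry the severity.

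Fourth, the consequence is small. Section 4.1 generally takes percentages over those with data, so the Week 56 row would remain a valid percentage on a smaller denominator, and nothing in the SAP tests it. Agreed.

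Finally, the conflict with the LTE SAP does not reach placebo subjects in general, whose LTE windows count from their first aducanumab dose. The exception would be placebo subjects dosed with aducanumab by accident, who fit the wording of the early-start column although LTE SAP Section 3.5.1 still classes them as late start. This should concern few subjects.

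**Conclusion.** The concern holds: Table 11 is wrong as written. It leaves 84 days unassigned and assigns one day twice, and the text has no rule that repairs either. These counts come directly from the printed table.

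The number of samples affected cannot be derived from the document. If visits centre on target, somewhat under half of the Week 56 samples would be lost (43–49% across the models above). The figure falls towards zero if visits run well late and rises to 80% at the extreme examined, 3 days early on average with SD 3.

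Severity is minor. The damage is confined to the by-visit rows of a descriptive table for a tertiary safety endpoint, and it arises only if the table is programmed literally.

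**What to change.** In Table 11, change the Week 56 window to [309, 470] and open the Week 78 window at day 471, keeping its upper limit. This matches the early-start column of LTE SAP Table 7 and leaves no gap and no overlap. If strict midpoints are preferred, [309, 469] with Week 78 from 470 also works, but the two plans would then differ by one day.

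The cost is two numbers in one table. No other analysis changes.
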